## 9.16.2 Study Completed

At the completion of the 12-month follow-up visit, subjects will be exited from the study. The 12-month follow-up visit and exit visit should be combined, and both a 12-month follow-up CRF and a Study Exit CRF need to be completed.

## 9.16.3 Lost to Follow-up

A subject is considered to be lost to follow-up if at least two attempts to contact the subject are unsuccessful. If a subject fails to return for follow-up visits, the site will contact the subject at the last known telephone number and/or dialysis center of record. The method of attempt (e.g., one letter and one phone record, or two letters) must be documented in the subject's medical record. In addition, regulation set forth by the governing IRB must be followed.

[figure not shown]
If all reasonable attempts to locate the subject fail, the subject will be considered lost to follow-up. A Study Exit CRF should be completed.

## 9.16.4 Subject Chooses to Exit (i.e. Revokes Consent)

A subject can withdraw from the study at any time. If the subject wishes to exit from the study (i.e. the subject revokes consent), the study site is required to document the reason for exit on the Exit CRF. In addition, study sites shall follow the regulations set forth by the governing IRB.

## 9.16.5 Investigator Withdraws Subject

No subjects should be withdrawn by investigators unless compelling medical justification is present. It is recommended investigators discuss any withdrawals with the study team prior to withdrawing subjects. If an Investigator Withdrawal is necessary, the following data should be collected prior to subject withdrawal if possible:

- Reason for subject withdrawal
- Rationale and/or documented safety concern

## 10. Risks and Benefits

### 10.1 Potential Risks

Medtronic follows rigorous Quality Assurance and Control procedures throughout the life of a product, from the business analysis phase through development, market release, and post-market surveillance. As with any intravascular procedure there are risks such as vessel dissection, perforation and infection that can occur. The clinical risks of using the Ellipsys Vascular Access System are related to the ability to create and achieve AV Fistula maturation to support hemodialysis. Table 4 lists the events that can be reasonably associated with surgical or percutaneous AV fistula creation, chronic kidney disease, vascular intervention, or may result from the use of the Ellipsys Vascular Access System.

**Table 4: Potential Adverse Events**

Vascular Events	Local Tissue Effects	Systemic Events	Other

 
• Vessel spasm
 
• Perforation of target or adjacent vessels
 
• Dissection of target or adjacent vessels
 
• Aneurysm or pseudoaneurysm
 
• Other injury to artery or vein, including intimal injury and resultant hyperplasia
 
• Thrombosis - total or partial occlusion due to clot formation or blockage within vessel
 
• Venous insufficiency or engorgement
 
• Arterial or venous hypertrophy
 
• Arterial or venous stenosis
 
• Arterial Steal Syndrome
 
	
 
• Bleeding (hemorrhage), extravasation or hematoma at the fistula or catheter insertion site requiring intervention
 
• Pain at the catheter insertion site
 
• Soft tissue damage
 
• Bruising, hematoma
 
• Ischemia
 
• Hyperemia
 
• Nerve damage of the upper extremity
 
• Transient functional impairment
 
• Edema of upper extremity
 
	
 
• High output cardiac failure
 
• Myocardial infarction
 
• Clinically significant changes in blood pressure
 
• Embolization of air, tissue, device or thrombus
 
• Stroke or transient ischemic attack
 
• Pulmonary arterial hypertension
 
• Death
 
	
 
• Electrical shock
 
• Allergic reaction to medications or device materials
 
• Infection or sepsis
 
• Failure to create an AVF during index procedure
 

**Medtronic Business Restricted**

• Venous hypertension

• Secondary surgical intervention to repair vascular injuries

• Loss of site for percutaneous AV fistula creation

• Acute anastomotic or vessel disruption due to PTA or other catheter-based manipulation

			
--	--	--	--

There are no incremental risks introduced to the subject as a result of participation in this study.

## 10.2 Risk Minimization

Potential risks with this study are minimized by selecting Investigators who are trained in the use of the study device and trained to the study protocol, by clearly defining inclusion/exclusion criteria to ensure only appropriate subjects are enrolled. In addition, the investigator performs a continuous monitoring, assessment, and documentation of any risks.

## 10.3 Potential Benefits

The Ellipsys System may offer no benefit. The potential benefit of having an AV fistula created with the Ellipsys System is reduced side effects as compared to standard therapy. The information gained from this study may be of benefit to other persons with the same medical condition.

## 10.4 Risk-Benefit Rationale

As with any intravascular procedure there are risks such as vessel dissection, perforation and infection that can occur. The clinical risks of using the Ellipsys Vascular Access System are related to the ability to create and achieve AV Fistula maturation to support hemodialysis. In the premarket study, there were no unanticipated adverse events. The adverse events reported were generally comparable to those associated with using other interventional intravascular devices and with standard open surgical AV fistula creation. The materials, manufacturing processes, and sterilization methods are well characterized, and verification testing mitigated the likelihood of unexpected events.

Potential risks with this study are minimized by selecting Investigators who are trained in the use of the study device and trained to the study protocol, by clearly defining inclusion/exclusion criteria to ensure only appropriate subjects are enrolled. In addition, the investigator performs a continuous monitoring, assessment, and documentation of any risks.

Medtronic shall establish a CEC to independently review and evaluate subject health status, device performance, and identify any safety concerns regarding subjects' wellbeing. Medtronic has further minimized the possibility of risks by completing product testing prior to the use of the Ellipsys System in this clinical study, implementing quality control measures into production processes, providing

***Medtronic Business Restricted***

guidelines for subject selection and evaluation, and providing adequate instructions and labeling. The Indication, warnings, and contraindications are provided in the device IFU.

## 11. Adverse Events and Device Deficiencies

### 11.1 Adverse Events

AE definitions are provided in Table 5. For this post-market surveillance study, only those adverse events related to the device, procedure, or secondary procedures, and any serious adverse events are required to be reported (including SAEs, ADEs, and SADEs). Such events shall be collected throughout the study duration, starting at the time of signing the IC through study exit.

Reporting of these events to Medtronic will occur on an AE eCRF and should begin at the time of study enrollment. Each event must be reported separately. Documented pre-existing conditions are not considered AEs unless the nature or severity of the condition has worsened.

Any medication/treatment associated with the treatment of an AE must be reported

Subject deaths are also required to be reported. Refer to Section 11.5 for AE reporting requirements.

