**Table 1: Schedule of Assessments and Visit Windows**

Data Collection Requirement / Assessment	Baseline	Index Procedure	Post-Procedure / Discharge	1 Week (± 2 days)	4 Weeks (± 7 days)	3 Months (± 14 days)	6 Months (± 30 days)	12 Months (± 60 days)
Informed Consent	X							
Demographics, Clinical Evaluation, & Vital Signs	X							
Duplex Ultrasound	X 	X 	X	X	X	X	X	X
Study Procedure		X	X					
AVF Evaluation				X	X	X	X	X
Secondary Procedures 		X 	X	X	X	X	X	X
Hemodialysis Records					X 	X 	X 	X 
Subject Satisfaction (VAQ)							X	
Cannulator Satisfaction Survey						X	X	X
Adverse Events and Device Deficiencies 	X	X	X	X	X	X	X	X
Medications	X	X		X	X	X	X	X

The Baseline and Pre-procedure Duplex Ultrasounds are to be performed and assessed by the Investigator/designee only, they will not be submitted to the DUS Core Lab. Beginning with the post-procedure DUS exam through follow-up completion, all DUS images are to be performed according to the Ellipsys PS DUS Protocol and submitted to the DUS Core Lab for analysis.

Additional procedures needed to mature or maintain the AVF or re-establish flow to meet the prescribed dialysis parameters. The need for such procedures will be assessed subsequent to completion of the AVF creation procedure.

Collection through successful 2-needle access of study AVF for >2/3 of sessions over a continuous 28-day period.

Adverse Event and Device Deficiencies assessment is required from the moment the subject is enrolled in the study (i.e. subject signed and dated the informed consent form).

 If an adjunctive procedure is required during the AVF creation procedure, the details of the procedure will be documented on the Adjunctive/Secondary Procedure CRF and will indicate that the adjunctive procedure occurred during the AVF creation procedure.

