**Medtronic Business Restricted**

**CONFIDENTIAL**

056-F275 Rev E Clinical Investigation Plan Template

	NOTE: As stated in the Ellipsys System IFU (available separate from the CIP), PTA/balloon maturation procedures to increase flow to the optimal access vessel was required in 99% of the Ellipsys IDE study subjects overall. The majority of these were performed to increase the anastomosis and juxta-anastomotic diameter and were unrelated to any clinical pathology. It is expected that similar procedures will be performed by the study investigator post-procedure and designated as such on the Secondary Procedure Form.
Cannulation	Adverse events directly related to cannulating a mature AV fistula target vessel to conduct dialysis, or other complications that can occur during or after dialysis such as bleeding, hematoma, etc.

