## 11.5 Reporting of Adverse Events

The investigator is required to assess and document in the medical record all SAEs, ADEs, SADEs, and DDs (per the definitions in Table 5) observed in subjects from the time of study enrollment. AEs shall be followed until the event has resolved or until study exit. In case of permanent impairment, the event shall be followed until the event stabilizes and the overall clinical outcome has been ascertained.

Reporting of AEs and DDs shall end once the subject exits the study. In any case where AEs are unresolved at the time of study exit, this shall be documented on the eCRF.

The investigator is responsible for reporting AEs to Medtronic and their local IRB (per IRB reporting requirements) as outlined in Table 7 below, by completing the Adverse Event eCRF and/or Device Deficiency eCRF. For the purposes of this CIP, planned/elective procedures for pre-existing conditions are not considered or reported as AEs as long as the pre-existing condition is not aggravated or exacerbated after a study procedure. A list of AEs that may be associated with the device and/or the interventional procedure is provided in Section 10.1.

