4.2.1 Secondary Endpoints

The following secondary endpoints to be evaluated in this study are as follows:

1. Primary patency through 12 months post-AVF creation:

Defined as freedom from access thrombosis or any intervention designed to facilitate, maintain or reestablish patency measured from time of access creation through 12 months.

2. Assisted primary patency through 12 months post-AVF creation:
Defined as freedom from access thrombosis from time of access creation through 12 months.
3. Secondary procedure Rate:
Defined as the percentage of subjects having one or more surgical or percutaneous interventions designed to mature or maintain the AVF or re-establish flow. Secondary procedures are procedures subsequent to completion of the AVF creation procedure. This endpoint will also be summarized by type of procedure, indication, procedure success and association with any adverse events (AEs).
4. Overall patient safety:
A full characterization of all adverse events during the study.

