7.8.3 Secondary Objective #4

Overall patient safety

Analysis Dataset:

Safety Analysis Set per section **Error! Reference source not found..**

Analysis Method:

Study-related AEs occurring during the study will be presented for the Safety population cumulatively and for each of the following study intervals:

Peri-operative: within 7 days (≤ 7 days) of the AVF creation procedure

Post-operative: 8 days to 3 months after the AVF creation procedure

Follow-up: more than 3 months after the AVF creation procedure

AEs will be summarized as the number of events as well as the number and percentage of subjects experiencing one or more of the following event types:

- Any study-related AE:
 - Cumulative
 - Peri-operative
 - Post-operative
 - Follow-up
- AE related to:
 - study device
 - study procedure
 - intra-procedure (index) or planned balloon angioplasty (PTA) maturation procedures
- Cannulation-related AE
- AE resulting from or related to a secondary procedure
- SAE
- UADE
- Stenosis

SAE incidence will be summarized by system organ class and event as the number of events as well as the number and percentage of subjects experiencing each event. The above summaries will be presented cumulatively and for each study interval. For the four different study intervals, subjects are included in the denominator of percentage calculations if their follow-up has extended at least to the beginning of that study time interval. Non-SAE will be presented in manner similar to SAE.

Endpoint Definition:

All adverse events related to the device, procedure, secondary procedures to maintain or re-establish patency, or any serious adverse event shall be reported. An independent CEC will assess and adjudicate any potential relationship to the device and/or procedures per the criteria set in the CEC charter. Stenosis events will be reported based on the MedDRA terms AVF site stenosis or AVF occlusion.

Additional Analysis:

- To assess the safety of the AVF creation procedure, rates for SAEs, UADEs, and procedure-related AEs will be descriptively compared to the pre-market study (DEN170004) results by presenting the rate and 97.5% CI for each study (CI adjusted for multiple comparisons). This comparison will be presented for the peri-operative and post-operative study intervals. If there are differing representations of baseline characteristics between the two studies, they will be adjusted for in the analysis.

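### AE reporting rules conflict with each other and with the planned tables: non-serious cannulation AEs are tabulated but not reportable, and non-serious procedural AEs have no Table 7 row or deadline

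*Protocol*

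**What the plan says.** **Reporting rules.** Protocol 11.1 sets the scope: "only those adverse events related to the device, procedure, or secondary procedures, and any serious adverse events are required to be reported". It then refers to 11.5 for the reporting requirements. Section 11.5 states: "The investigator is required to assess and document in the medical record all SAEs, ADEs, SADEs, and DDs", using the Table 5 definitions, and sends reporting to the sponsor through Table 7. Table 7 has rows for SAE, ADE, SADE, device deficiency, and a deficiency that could have led to a SADE. Table 5 ties an ADE to use of the device.

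**Relatedness classes.** Table 6 (section 11.4) separates the device, the index procedure, secondary procedures, intra-procedure or planned PTA, and cannulation. The cannulation class begins: "Adverse events directly related to cannulating a mature AV fistula target vessel to conduct dialysis". Bleeding and hematoma are among its examples. Initial vessel access and wire exchanges that do not involve the device belong to the index procedure, not the device.

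**Analysis.** Protocol 13.3.4 and SAP 7.8.3 define the Secondary Objective #4 endpoint with the 11.1 scope, which includes procedure- and secondary-procedure-related AEs but does not name cannulation. Both then list "Cannulation-related AE" among the event types, with no seriousness limit, and say that non-serious events are presented in the same way as serious ones. SAP 7.8.3 adds that "rates for SAEs, UADEs, and procedure-related AEs will be descriptively compared to the pre-market study (DEN170004) results", for the peri-operative and post-operative intervals, with 97.5% CIs.

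**The concern.** A table can show only what sites were told to report. Here the planned tables are wider than the reporting rules in one place, and the reporting rules disagree with one another in another.

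The cannulation row is headed as though it covers all such events. If the rules are followed as written, it would hold serious events, events also judged related to the device or a procedure, and whatever sites volunteer. A reader would take that as the total.

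For procedural AEs, 11.1 and the section with the deadlines give a site two different lists. A site working from Table 7 could leave out a non-serious access-site hematoma that appears after the procedure, and believe it had complied. Section 9.15 treats late AE reporting as a deviation, but lateness cannot be identified for a class with no deadline. The narrow list also recurs in the investigator records of 15.7.1.

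At stake are the completeness of Secondary Objective #4, which SAP 4.2.1 describes as "A full characterization of all adverse events during the study", and the reading of the procedure-related AE rate beside the pre-market result. A shortfall there would look like reassurance.

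**Working it through.** The point rests on no stated figure, so the check sets the passages side by side.

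| Event | 11.1 | 11.5 / Table 7 | Endpoint definition (13.3.4, SAP 7.8.3) | Tabulated (13.3.4, SAP 7.8.3) | Pre-market comparison |
|---|---|---|---|---|---|
| Any SAE | required | listed | included | yes | yes |
| Non-serious, device-related (ADE) | required | listed | included | yes | not as a class |
| Non-serious, index procedure only | required | **not listed** | included | yes | **yes** |
| Non-serious, secondary procedure only | required | **not listed** | included | yes | not stated |
| Non-serious, cannulation only | **not named** | **not listed** | **not named** | **yes** | no |

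**Step 1, cannulation.** The 11.1 scope is exclusive. Cannulation is a separate Table 6 class, so an event related only to it is neither device-, procedure- nor secondary-procedure-related. If it is non-serious, it is not an SAE or SADE. It is not an ADE, because an ADE needs a relation to use of the device. No section 11 rule therefore requires it, yet the analysis has a row for it.

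The version history suggests how this may have arisen. Version 2.0 narrowed the reportable set, version 3.0 added cannulation to Table 6, and the current 11.1 does not name it.

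**Step 2, procedural AEs.** Section 11.1, protocol 13.3.4 and SAP 7.8.3 agree that these are reportable whether serious or not. Section 11.5 and Table 7 give no class into which a non-serious, non-device event fits. This is a contradiction inside section 11, not an exclusion stated by the plan.

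**Step 3, how far other text fills the gap.**
- Section 9.8 sends intra-procedure AEs to the AE form whatever their seriousness. It covers the procedure itself only.
- Table 6 treats AEs within 30 days as index-procedure-related unless shown otherwise. This brings them under 11.1, but it does not make them ADEs and so does not put them in Table 7. Taking 3 months as day 90 (the Table 3 target), the post-operative interval runs from day 8 to day 90, which is 90 − 7 = 83 days. The default covers days 8 to 30, which is 30 − 7 = 23 days, and leaves 83 − 23 = 60 days without it.
- Section 9.6 asks for adverse events without restriction, which conflicts with the exclusive wording of 11.1.
- The cannulator survey has no complication field beyond needle attempts and free text.

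**Step 4, direction and size.** Let p be the true share of subjects with a procedure-related AE. Let s be the share of those subjects whose events are all non-serious and not device-related. Let m be the share of that group left unreported. Then

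observed rate = p × (1 − s × m).

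If every site follows 11.1, m = 0 and the observed rate is p, so there is no bias. If every site reports only what Table 7 lists, m = 1 and the observed rate is p × (1 − s). The shift is never upward. The documents give no value for p, s or m, so no figure is put on it.

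**The case against.** The strongest reply is that 11.1 requires procedure-related AEs, 13.3.4 and SAP 7.8.3 repeat it, and nothing says Table 7 overrides them. Section 9.8 captures intra-procedure events, Table 1 schedules AE assessment at every visit to 12 months, and the 30-day default covers the whole peri-operative interval. This stands. It is why the procedural part is a risk of under-ascertainment. A reader might infer that the procedure-related rate is biased low as a matter of fact, and the documents do not support that.

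A reader might also infer that the pre-market comparison is distorted. That would need broader AE collection in the pre-market study, and the documents do not give its collection rule. Cannulation AEs are not part of that comparison.

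A third tempting reading is that dialysis records stop just when cannulation starts. Table 1, footnote 3 says: "Collection through successful 2-needle access of study AVF for >2/3 of sessions over a continuous 28-day period". The first cannulations and the qualifying 28 days are therefore covered, the rule matches the functional cannulation endpoint, and the documents do not say that these records hold AE data. The footnote gives no support to this point.

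On cannulation, it can be said that Table 6 does not make its classes mutually exclusive, that an event graded as possibly related to the device or procedure is reportable, and that having the class suggests capture was intended. This narrows the gap to events related only to cannulation. It does not close it, because intent is not an instruction to sites.

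Finally, limited AE collection is a disclosed choice for a post-market study, and the endpoint definition says so. That is fair, but a limited choice should not feed a row headed as a total.

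**Conclusion.** The point holds as a conflict between rules and tables. Non-serious AEs related only to cannulation fall outside every reporting rule in section 11 but are tabulated, so that row would under-count if sites report only what is required. Non-serious AEs related to the index or a secondary procedure are required by 11.1 and the endpoint definitions, but have no row or deadline in 11.5 and Table 7. Their capture, including in the rate shown beside the pre-market study, depends on which passage a site follows.

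Any error is downward. For procedural events it may be zero, and its size cannot be derived from the documents. The conclusion assumes that sites do not routinely report beyond what they are told is required.

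The primary safety endpoints are not affected. Study-related SAEs are reportable under every passage, and early occlusion is adjudicated by the events committee, with ultrasound scheduled at discharge and 1 week. This should be corrected, but it does not threaten the study's main results.

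**What to change.** Make 11.1, 11.5 and Table 7 list one reportable set: all SAEs, plus all AEs, serious or not, related to the device, the index procedure, intra-procedure or planned PTA, a secondary procedure, or cannulation. Give the related AEs that are not device effects their own Table 7 row and deadline. Bring the endpoint definitions in protocol 13.3.4 and SAP 7.8.3 into line.

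If the sponsor decides not to collect non-serious cannulation AEs, relabel the row in protocol 13.3.4 and SAP 7.8.3 as *Serious cannulation-related AE*, so that it is not read as a total. The 11.5 and Table 7 correction for procedural events is needed either way.

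The cost is wording changes, site retraining, more AE forms and higher reported AE counts. If the change takes effect after some subjects have been followed, counts before and after it are not on the same footing, and the report should say so. Relabelling alone costs almost nothing but gives up the non-serious cannulation information.
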